Therapeutic plasma exchange (TPE) offers an immediate and scientifically grounded intervention for the removal of a host of pathogenic antibodies and toxic molecules by centrifugal separation of plasma or plasma membrane filtration. Xiao⁵ and colleagues successfully incorporated TPE in the management of a patient with severe CRS following CAR-T treatment in conjunction with Tocilizumab and steroids with daily documentation of cytokine levels.

Precedence for consideration of TPE in a variety of inflammatory dominant disease states is well known. Interest in adjuvant treatment for management of sepsis and multi organ dysfunction is reflected in Busund⁶ and Rimmer⁷ manuscripts. Patel et al⁸ successfully used TPE in three pediatric patients with pH1N1 influenza A acute respiratory failure and hemodynamic shock despite failure of best supportive care. All three survived with “good functional recovery.”

Ruxolitinib is a JAK/STAT pathway inhibitor which is FDA approved for polycythemia rubra vera, myelofibrosis and graft versus host disease. Kenderion et al⁹ reported a murine model of CRS following CAR-T cellular therapy with marked elevation of IL-6, interferon-gamma, TNF alpha mimicking human CAR-T therapy induced CRS. Ruxolitinib treated mice demonstrated clinical amelioration and decrement in inflammatory cytokines. Incyte Corporation has announced plans to launch a Phase III trial of single agent ruxolitinib for COVID-19 associated cytokine storm.

This protocol will evaluate the efficacy of TPE alone or in combination with ruxolitinib in COVID positive patients with PENN grade 2, 3, 4 CRS. It is hypothesized that dual intervention of acute aphaeretic depletion of cytokines and concomitant suppression of production will produce superior amelioration of the cytokine load and to help to prevent cytokine load rebound. This protocol is envisioned as a pilot study (n=20) for hypothesis generation for future investigation.

Primary Endpoints

1. To document the efficacy of TPE alone or in conjunction with ruxolitinib in decreasing the cytokine load over a 14-day intervention study
2. Analysis of all therapy related adverse events (AEs)

Secondary Endpoints

1. To correlate the clinical course of participants with the degree of specific cytokine reductions
3. To calculate time to independence from mechanical ventilation
4. To calculate time to independence from supplemental oxygen therapy

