5. To measure CRP, ferritin and cytokine levels (IL-6, IL-8, IL-10, TNF α , IFN γ , GM-CSF) to map the cytokine landscape over the course of the study
6. To explore correlative biomarker studies
7. To bank plasma and other blood derivatives in the Prisma Health ITOR Biorepository for future investigation

Study Design

Study type:	Interventional Pilot Clinical Trial
Estimated Enrollment	20 patients
Allocation	Two sequential cohorts, 10 patients per cohort First 10 patients will receive TPE alone (Cohort 1A) Second 10 patients will receive TPE in combination with ruxolitinib
Masking	None (open label)
Primary purpose	Treatment efficacy
Official title:	Interventional Study to Evaluate the Efficacy of Therapeutic Plasma Exchange (TPE) Alone or in Combination with Ruxolitinib in COVID-19 Positive Patients with PENN Grade 2, 3, 4 Cytokine Released Syndrome (CRS)

Study Population

COVID-19 positive patients with PENN grade 2, 3, 4 CRS and respiratory failure.

Eligibility

Inclusion:

1. Patients positive for COVID-19 by PCR or alternative accepted methodology
2. PENN class 2,3,4 CRS¹⁰
3. Respiratory insufficiency with supplemental oxygen to maintain O2 sat greater than 89%
4. Clinically positive imaging by CXR or CT scan with evidence of bilateral pulmonary infiltrates, ground glass opacification or other pattern of consolidation felt likely to be linked to COVID infection or complication thereof
5. Adults 22 years of age or older

Exclusion:

1. Pregnancy
2. Breast feeding
3. Class 3-4 NYHA heart failure
4. Current use of synthetic disease modifying anti-rheumatic drugs (DMARDs), with the exception of hydroxychloroquine, or IL-6 inhibitors or other immunosuppressive therapies outside of number five below
5. Current use of chronic corticosteroids if in excess of prednisone 10mg per day or equivalent
6. Suspected or confirmed clinically significant bacterial infection
7. History of TB
8. History of HIV
9. History of IBD
10. JAK inhibitor use within last 30 days
11. Creatinine clearance less than 15 ml / min
12. Absolute neutrophil count < 1000
13. Platelet count < 50,000
14. AST or ALT > 5 times the upper limit of normal
15. Clinical assessment that TPE or ruxolitinib could pose unacceptable risk by study participation or the treatment is deemed inappropriate by a study investigator
16. Current enrollment on another investigational protocol for COVID-19 induced CRS

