17. Stage 4 obstructive lung disease with chronic hypoxic respiratory failure requiring supplemental O2 at baseline, or ILD with chronic hypoxic respiratory failure requiring supplemental O2 at baseline

Treatment Plan

Device: Spectra Optia Apheresis System

Intended Use of Device: Therapeutic Plasma Exchange performed per marketed labeling

Drug: Ruxolitinib (generic) marketed as brand name, Jakafi ,manufactured by Incyte Corporation, will be used per the marketed package insert.

Cohort 1A: TPE, five single plasma volume exchanges over 7 days (every day x 2 then every other day x 3) with albumin or FFP replacement if underlying coagulopathy per institutional protocol (Appendix A).

Other – standard medical care

Cohort 1B: TPE as in cohort 1A combined with ruxolitinib 5mg po BID beginning day prior to first TPE and continuing BID for total of 14 days. On days of TPE, ruxolitinib dosing will be immediately post procedure and a second dose approximately 8 hours later.

Other – standard medical care

Schedule of Assessments

Pre Treatment

Standard of Care Assessments

- Complete Blood Count (CBC)
- Comprehensive Metabolic Panel (CMP)
- C-Reactive Protein (CRP)
- Ferritin
- lipid panel
- Hepatitis B Surface Antigen, Hepatitis B Surface Antibody, Hepatitis B Core Antibody and Hepatitis C Antibody
- PT/INR
- Partial Thromboplastin Time (PTT)
- Fibrinogen
- type and screen
- serum pregnancy test
- physical examination

Study Related Assessments

- cytokine panel
- peripheral blood for biorepository
- peripheral blood for pharmacogenomics

During Treatment (On Study)

Standard of Care Assessments

- daily CBC
- daily CRP
- PaO₂/FiO₂ ratios days (with ABGs) per Appendix B
- amount of supplemental O₂, SPO₂%, respiratory rate, imaging per MD discretion (*for non-intubated patients*)
- measure daily SPO₂%, FiO₂; PEEP; and lung compliance (inspiratory pause – V_t/P_{plat} – PEEP) or plateau pressures (*mechanically vented patients*)
- daily Basic Metabolic Panel (BMP)
- physical examination

Study Related Assessments

- daily collection of study related adverse events and/or serious adverse events
- Fibrinogen (on days of TPE only)
- daily cytokine panel and GM-CSF
- repeat cytokine panel and GM-CSF within 60 minutes post TPE (on days of procedure only)
- serum ferritin per Appendix B
- peripheral blood and plasma waste for biorepository per Appendix B
- day 28 office visit or virtual health visit to assess clinical status of the patient

Risk Analysis

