Standard statistical methods will be employed to analyze all data. It is anticipated that the following techniques may be used: descriptive statistics, t-test, Chi-square, Fisher’s exact test, Kaplan-Meier analysis, and graphical displays. This protocol may not reflect all analyses planned for the study; additional analyses may be conducted for observational purposes only.

Summary statistics will consist of numbers and percents of responses in each category for discrete measures, and of mean, n, standard deviation, median, minimum, maximum and 95% confidence intervals for continuous measures.

Sample Size Determination

The initial sample size is 20. Each cohort will enroll 10 patients. This number is considered sufficient for an exploratory pilot study to provide information for planning further investigations.

Analysis of Safety

The safety evaluation will compare the proportion of Subjects in each treatment group who exhibit treatment-related adverse effects. These adverse events will be presented for individual patients as a listing of events.

Dissemination of Results

Results of this study may be used for presentations, posters, publications, or extramural grant applications. The publication will not contain any identifiable information that could be linked to a study patient.

References

<https://doi.org/10.1038/s41586-020-2012-7>
2. World Health Organization. Novel coronavirus situation report-2. January 22, 2020.
<https://www.who.int/docs/default-source/coronavirus/situation-reports/20200122-sitrep-2-2019-ncov.pdf> (Accessed on April 7, 2020).
3. P. Conti, G. Ronconi, A. Caraffa, C. Gallenga, R. Ross, I. Frydas, S. Kritas. Induction of pro-inflammatory cytokines (IL-1 and IL-6) and lung inflammation by COVID-19: anti-inflammatory strategies. *J Biol Regul Homeost Agents*. 2020 Mar 14; 34(2).
4. Puja Mehta, Daniel F McAuley, Michael Brown, Emilie Sanchez, Rachel S Tattersall, Jessica J Manson. COVID-19: consider cytokine storm syndromes and immunosuppression. *The Lancet*. 28 March–3 April 2020.

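### The only named between-cohort safety comparison rests on unblinded attribution with no relatedness cut-off; a descriptive laboratory table and graded all-cause AEs should sit beside it

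*Combined protocol and SAP*

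**What the plan says.** Analysis of Safety (Statistical Analyses) states that the evaluation will "compare the proportion of Subjects in each treatment group who exhibit treatment-related adverse effects", followed by a patient listing of those events. The second primary endpoint is likewise confined to therapy-related AEs.

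Four other provisions bear on what reaches that comparison:

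- **Design.** Study Design gives no masking and two sequential cohorts of 10: TPE alone, then TPE plus ruxolitinib.
- **Collection.** The on-treatment assessments include "daily collection of study related adverse events and/or serious adverse events".
- **Definition.** The Adverse Events section defines an AE as a medical problem that is *unexpected*. It grades by CTCAE v5.0 and reports relatedness, to the study drug or the study therapy, as not, possibly, likely or related. No section says which levels make an event treatment-related.
- **Laboratory data.** Appendix B schedules a CBC and a BMP daily in both cohorts. General Statistical Considerations gives generic summary statistics and leaves room for additional analyses. No laboratory shift, grade or nadir table is named.

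**The concern.** A follow-on study would look to the 1A versus 1B contrast to judge whether adding ruxolitinib costs blood counts or renal function. As planned, the contrast counts only events that an unblinded investigator has attributed to treatment, and the threshold for attribution is left open. Two analysts could take different cut-offs and report different results for a primary endpoint from the same data.

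The wording upstream narrows the data as well. Read literally, a fall in platelets or neutrophils that the dose-modification rules already anticipate is not unexpected, and a non-serious event judged unrelated is not study related. Either could go unrecorded as an AE. In patients with COVID-19, CRS and respiratory failure, many abnormalities have a plausible disease cause, so attribution is a real judgement and could differ between the cohorts. The result could be a descriptive safety difference that is created, hidden or left incomplete.

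**Working it through.** **1. The plan's own figure.** The only number is the sample size, 10 + 10 = 20. No AE rate, alpha or power is given, so there is nothing further to reproduce. One patient is 1/10, or 10 percentage points, of a cohort.

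**2. What could be counted without attribution.** Appendix B runs days 1-15 in cohort 1A and days 0-14 in cohort 1B, so days 1-14 are common. That gives at most 14 x 20 = 280 CBCs and 280 BMPs, if nobody dies and no draw is missed. The exclusions "Platelet count < 50,000" and "Absolute neutrophil count < 1000" lie above the ruxolitinib dose-modification thresholds (platelets 25,000-35,000 and below 25,000; ANC below 500). No eligible patient starts beyond those thresholds, so a crossing on study is new since screening and needs no causality judgement.

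**3. Illustration of attribution effects (all rates assumed).** Let cohort c have a true proportion affected t_c and a probability q_c that an affected patient is called related. Then X_c ~ Binomial(10, t_c q_c). The quantity is P(X_1B - X_1A >= 2), by exact enumeration. The two-patient criterion is mine, chosen for illustration. Attribution-free means q = 1 in both cohorts.

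| Attribution 1A/1B | No true difference, 20% | 30% | 40% | True 20% v 40% | True 10% v 30% |
|---|---|---|---|---|---|
| Attribution-free | 0.20 | 0.23 | 0.25 | 0.60 | 0.61 |
| 50/50 | 0.12 | 0.17 | 0.20 | 0.37 | 0.33 |
| 40/60 | 0.19 | 0.28 | 0.34 | 0.52 | 0.45 |
| 60/40 | 0.07 | 0.09 | 0.10 | 0.23 | 0.22 |
| 20/80 | 0.39 | 0.57 | 0.70 | 0.79 | 0.68 |

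With no true difference, a 40/60 gap adds nothing at 20% and about 5 to 10 points at 30-40%. Only 20/80 creates a large spurious excess. With a true 20% v 40%, equal attribution of half the events halves the expected difference (10% v 20%), and 60/40 leaves 12% v 16%. Two-sided Fisher p <= 0.05 occurs in at most 13% of trials in every case shown, so the harm is a misleading description and seldom a significant test.

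**4. Would a single any-AE row cure it?** Assume a background proportion b with any AE in both cohorts, and that ruxolitinib independently causes an AE in 20% of patients. All-cause proportions are b in 1A and 1 - 0.8(1 - b) in 1B. For comparison, take a related row in which 40% of background events are called related in both cohorts: 0.4b v 1 - 0.8(1 - 0.4b).

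| Background b | All-cause 1A v 1B | P(at least 2 more), all-cause | P(at least 2 more), related row |
|---|---|---|---|
| 20% | 0.20 v 0.36 | 0.52 | 0.58 |
| 50% | 0.50 v 0.60 | 0.41 | 0.52 |
| 80% | 0.80 v 0.84 | 0.26 | 0.48 |
| 90% | 0.90 v 0.92 | 0.14 | 0.46 |

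Perfect attribution (0 v 0.20) gives 1 - 0.8^10 - 10 x 0.2 x 0.8^9 = 1 - 0.107 - 0.268 = 0.62 at every background. An ungraded any-AE row is therefore a poor remedy if background events are common. Graded laboratory values and higher-grade AEs are less exposed to this ceiling.

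**The case against.** The strongest case against is that much of this is already covered. The relatedness scale includes a not-related level, so summing the levels would give an all-cause count, and a strict reading of study-related collection would leave that level nearly empty. All SAEs go to the manufacturer whatever the causality assessment. The DSMB reviews SAEs and all cohort 1A outcomes before 1B opens. The generic summaries include minima and maxima, and additional analyses are allowed. Much of this stands as mitigation: unrelated events are probably recorded to some extent. None of it, however, specifies a comparison between cohorts that is free of attribution, and the SAE route covers serious events only.

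It is also fair that large distortion needs a strong attribution gap for which the documents give no evidence, and that a single any-AE row may be near its ceiling in such ill patients. The second point stands and shapes the fix.

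Three stronger readings are tempting and unsupported:

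- A reader might infer that attribution will run against ruxolitinib because the on-study laboratory rules act only on that drug. Those rules are numeric thresholds applied whatever the cause, and relatedness may be to the study therapy, so TPE can be blamed in either cohort.
- A reader might infer that every value needed is already scheduled. Platelets, haemoglobin and creatinine are. Appendix B does not say that the CBC includes a differential; Appendix A lists one daily in the plasma plan and once in the albumin plan. AST/ALT would need the CMP, which Appendix B marks at screening only. A full all-cause AE count needs the collection and definition wording changed.
- A reader might infer that an attribution-free table would isolate a ruxolitinib effect. Sequential enrolment still confounds cohort with calendar time.

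**Conclusion.** The point holds as a gap in specification. The single named safety contrast depends on unblinded attribution with no cut-off, and the collection and definition wording may exclude known toxicities and non-serious unrelated events. The size and direction of any distortion are unknown. The illustrations rest on assumed event rates, assumed attribution probabilities, independence between patients and a two-patient criterion; they show that the effect can range from negligible to large. What follows from the documents alone is that one reclassified patient is worth 10 points and that attribution-free blood counts and creatinine are already scheduled. The weight is minor: this is a 20-patient pilot meant to generate hypotheses, and nothing here decides the trial.

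**What to change.** 1. **Related AEs.** Keep the related-AE proportion and listing in Analysis of Safety, and state that possibly related, likely related and related all count as treatment-related.
2. **Laboratory table.** Add a descriptive table by cohort, regardless of attribution and with no test. Show worst post-baseline CTCAE v5.0 grade and shift from screening over days 1-14 for platelets, haemoglobin and creatinine, and for ANC where a differential exists. Give the numbers of patients and days with a value. Add counts in both cohorts of patients crossing the dose-modification thresholds: platelets 35,000 or below, platelets below 25,000, and ANC below 500.
3. **All-cause AEs.** Before cohort 1A enrols, amend the collection and definition wording trial-wide to remove *study related* and *unexpected*. Report all-cause AEs by cohort and CTCAE grade, for example grade 3 or higher, beside the related AEs and not in place of them.

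**Cost.** One paragraph and one table for items 1 and 2, with no added samples, visits or patients. Item 3 is a small protocol amendment needing IRB approval, with slightly more AE recording. If cohort 1A has already started, AE capture would differ between cohorts; the cut-off and the laboratory table would still be useful. COVID-19-caused abnormalities will be counted too, so the added rows describe the cohorts and cannot establish causation.

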APPENDIX A:**TPE-Plasma Therapy Plan**

Apheresis Orders	Frequency

 Therapeutic Plasma Apheresis with Plasma Replacement 	As Ordered
IV Access	

 Initiate peripheral IV Protocol 	Daily

 Access Central Venous Catheter 	Daily

 Access A/V Fistula for Procedure 	Daily
Pre-Procedure Labs (Baseline)	

 CBC with Differential 	Once

 CMP 	Once

 LDH 	Once

 Haptoglobin 	Once

 PT/INR 	Once

 PTT 	Once

 Reticulocyte Count 	Once

 ADAM TS 13 Activity 	Once

 Type and Screen 	Once

 Bilirubin Total and Direct 	Once

 Prepare Plasma 	Once
Labs	

 CBC with Differential 	Daily

 CMP 	Daily

 LDH 	Daily

 Haptoglobin 	Daily
Anticoagulant Prime	

 Anticoagulant citrate dextrose injection 500 ml 	PRN
Medications	

 diphenhydramine (Benadryl) 25 mg IV 	Once

 calcium gluconate 3g in NS 250ml IV 	Once

 calcium gluconate 3g in NS 250ml IV 	PRN

 calcium carbonate tablet 1500 mg PO 	PRN

 alteplase 2mg in 10ml syringe 	PRN clot clearance
Hypersensitivity Regimen	

 at any sign of anaphylaxis, stop infusion, notify MD and administered prescribed medications 	PRN

 diphenhydramine (Benadryl) 50 mg IV 	PRN

 methyleprednisolone (Solu-Medrol) 40 mg IV 	PRN

 famotidine (Pepcid) 20 mg IV 	PRN
Nursing Orders	

 Transfuse Plasma 	Once

TPE-Albumin Therapy Plan

Apheresis Orders	Frequency

 • Therapeutic Plasma Apheresis with Albumin Replacement 	As Ordered
IV Access	

 • Initiate peripheral IV Protocol 	Daily

 • Access Central Venous Catheter 	Daily

 • Access A/V Fistula for Procedure 	Daily
Pre-Procedure Labs (Baseline)	

 • CBC with Differential 	Once

 • CMP 	Once

 • Fibrinogen 	Once
Anticoagulant Prime	

 • Anticoagulant citrate dextrose injection 500 ml 	PRN
Medications	

 • calcium carbonate tablet 1000 mg PO 	PRN

 • calcium gluconate 2.5g in NS 250ml IV 	PRN

 • alteplase 2mg in 10ml syringe 	PRN clot clearance
Hypersensitivity Regimen	

 • at any sign of anaphylaxis, stop infusion, notify MD and administered prescribed medications 	PRN

 • diphenhydramine (Benadryl) 50 mg IV 	PRN

 • methyleprednisolone (Solu-Medrol) 40 mg IV 	PRN

 • famotidine (Pepcid) 20 mg IV 	PRN
Nursing Orders	

 • Infuse Albumin 	Once

Appendix B: COHORT 1A Schedule of Assessments: Therapeutic Plasma Exchange alone

Assessment	Screening (24 hours)	Study Day															
		1	2	3	4	5	6	7	8	9	10	11	12	13	14	15	28
Informed Consent and Medical History	X																
Physical Examination ^a	X	X	X	X	X	X	X	X	X	X	X	X	X	X	X	X	X
Complete Blood Count (CBC)	X	X	X	X	X	X	X	X	X	X	X	X	X	X	X	X	
Comprehensive Metabolic Panel (CMP)	X																
Basic Metabolic Panel (BMP)		X	X	X	X	X	X	X	X	X	X	X	X	X	X	X	
C-Reactive Protein (CRP)	X	X	X	X	X	X	X	X	X	X	X	X	X	X	X	X	
Ferritin	X			X			X			X					X		
Hepatitis Serology ^b	X																
Lipid Panel ^b	X																
PT/INR	X																
PTT	X																
Fibrinogen	X	X	X		X		X		X								
Type and Screen ^b	X																
Serum Pregnancy Test ^b	X																
Cytokine Panel (IL-6, IL-8, IL-10, TNF α , IFN γ) ^c	X	X	X	X	X	X	X	X	X	X	X	X	X	X	X	X	
GM-CSF ^c	X	X	X	X	X	X	X	X	X	X	X	X	X	X	X	X	
Peripheral Blood for biorepository	X					X			X								X
Peripheral Blood for pharmacogenomics	X																
PaO ₂ /FiO ₂ ratios (with ABGs) - (mechanically vented patients only)		X		X		X											
Supplemental O ₂ , SPO ₂ %, Respiratory Rate, Imaging at MD discretion (for NON-intubated patients)		X	X	X	X	X	X	X	X	X	X	X	X	X	X	X	
SPO ₂ %, FiO ₂ , PEEP, Lung compliance (inspiratory pause - Vt/Pplat-PEEP) or plateau pressures (mechanically vented patients only)		X	X	X	X	X	X	X	X	X	X	X	X	X	X	X	
Therapeutic Plasma Exchange (TPE) (plus waste for biorepository)		X	X		X		X		X								

^a If patient is discharged from the hospital, daily physical examination will not be required. Perform one physical exam prior to the patient’s last study visit. Day 28 may be a virtual visit if needed.

^b Hepatitis serology, Lipid panel, Type and Screen, Serum Pregnancy Test acceptable within 7 days prior to enrollment.

^c Cytokine Panel and GM-CSF are to be repeated within 60 minutes post TPE on days of plasma exchange procedure only.

Appendix B: COHORT 1B Schedule of Assessments: Therapeutic Plasma Exchange Plus Ruxolitinib																	
Assessment	Screening (24 hours)	Study Day															
		0	1	2	3	4	5	6	7	8	9	10	11	12	13	14	28
Informed Consent and Medical History	X																
Physical Examination ^a	X	X	X	X	X	X	X	X	X	X	X	X	X	X	X	X	X
Complete Blood Count (CBC)	X	X	X	X	X	X	X	X	X	X	X	X	X	X	X	X	X
Comprehensive Metabolic Panel (CMP)	X																
Basic Metabolic Panel (BMP)		X	X	X	X	X	X	X	X	X	X	X	X	X	X	X	X
C-Reactive Protein (CRP)	X	X	X	X	X	X	X	X	X	X	X	X	X	X	X	X	X
Ferritin	X			X				X			X					X	
Hepatitis Serology ^b	X																
Lipid Panel ^b	X																
PT/INR	X																
PTT	X																
Fibrinogen	X		X	X		X		X		X		X					
Type and Screen ^b	X																
Serum Pregnancy Test ^b	X																
Cytokine Panel (IL-6, IL-8, IL-10, TNF α , IFN γ) ^c	X	X	X	X	X	X	X	X	X	X	X	X	X	X	X	X	X
GM-CSF ^c	X	X	X	X	X	X	X	X	X	X	X	X	X	X	X	X	X
Peripheral Blood for biorepository	X					X				X							X
Peripheral Blood for pharmacogenomics	X																
PaO ₂ /FiO ₂ ratios (with ABGs) - (mechanically vented patients only)		X		X		X											
Supplemental O ₂ , SPO ₂ %, Respiratory Rate, Imaging at MD discretion (for NON-intubated patients)		X	X	X	X	X	X	X	X	X	X	X	X	X	X	X	X
SPO ₂ %, FiO ₂ , PEEP, Lung compliance (inspiratory pause - Vt/Pplat-PEEP) or plateau pressures (mechanically vented patients only)		X	X	X	X	X	X	X	X	X	X	X	X	X	X	X	X
Therapeutic Plasma Exchange (TPE) (plus waste for biorepository)			X	X		X		X		X							
Ruxolitinib Dosing		X	X	X	X	X	X	X	X	X	X	X	X	X	X	X	X

^a If patient is discharged from the hospital, daily physical examination will not be required. Perform one physical exam prior to the patient's last study visit. Day 28 may be a virtual visit if needed.

^b Hepatitis serology, Lipid panel, Type and Screen, Serum Pregnancy Test acceptable within 7 days prior to enrollment.

^c Cytokine Panel and GM-CSF are to be repeated within 60 minutes post TPE on days of plasma exchange procedure only.

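### Several rows of the cohort 1B table in Appendix B are out of line with cohort 1A and with the protocol text, so PaO2/FiO2, the first ferritin and the first on-study banked sample lose day-matched comparison

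*Combined protocol and SAP*

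**What the plan says.** The Treatment Plan gives cohort 1A "five single plasma volume exchanges over 7 days (every day x 2 then every other day x 3"), and cohort 1B the same exchanges. Ruxolitinib in 1B is given "beginning day prior to first TPE and continuing BID for total of 14 days". The 1B table therefore has a day 0 and runs from day 0 to 14; the 1A table runs from day 1 to 15. Both add screening and day 28.

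The Schedule of Assessments in the text does not fix the days for the measures at issue. It lists "serum ferritin per Appendix B" and "peripheral blood and plasma waste for biorepository per Appendix B", and refers to the same appendix for PaO2/FiO2, where the row in both tables is labelled "ratios (with ABGs) - (mechanically vented patients only"). It does limit on-treatment fibrinogen to exchange days, and it describes day 28 as a check of clinical status, in person or remote, with no laboratory test named. Footnote a of the tables repeats the last point: "Day 28 may be a virtual visit if needed".

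Secondary endpoint 5 begins "To measure CRP, ferritin and cytokine levels". Another secondary endpoint relates clinical course to cytokine reductions.

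**The concern.** The tables are the only source for these sampling days, so staff would follow them as printed. In cohort 1B some marks sit on the correct day relative to the exchanges, while others sit one day earlier than in 1A. PaO2/FiO2 is the only scheduled arterial oxygenation measure, and only ventilated patients, out of 10 per cohort, contribute to it. With so few values, a mismatch in days is hard to adjust for afterwards.

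The day-28 column raises a separate problem. Blood tests are marked in one cohort only, at a visit that may be remote, and the same column carries a drug-dosing mark. A study that hypothesises less cytokine rebound with the combination would want late cytokines in both cohorts or in neither.

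**Working it through.** No sample-size or power figure is involved. The check maps each mark to its column heading (1A: screening, days 1 to 15, 28; 1B: screening, days 0 to 14, 28) and compares the days. Every row compared has 17 cells.

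**Anchor.** The row "Therapeutic Plasma Exchange (TPE) (plus waste for biorepository") falls on days 1, 2, 4, 6, 8 in both tables: two consecutive days, then every other day three times, as the text says. A day number therefore means the same thing relative to the exchanges in both cohorts.

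**Days marked after screening**

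| Row | 1A | 1B | Shared |
|---|---|---|---|
| TPE | 1, 2, 4, 6, 8 | 1, 2, 4, 6, 8 | 5 of 5 |
| PaO2/FiO2 | 1, 3, 5 | 0, 2, 4 | 0 of 3 |
| Ferritin | 3, 6, 9, 14 | 2, 6, 9, 14 | 3 of 4 |
| Banked blood | 5, 8, 28 | 4, 8, 28 | 2 of 3 |
| Fibrinogen | 1, 2, 4, 6, 8 | 1, 2, 4, 6, 8, 10 | 5, plus day 10 in 1B |
| CBC, BMP, CRP, cytokines, GM-CSF, two daily respiratory rows | 1–15 | 0–14, 28 | 14 (days 1–14) |
| Ruxolitinib dosing | – | 0–14, 28 | – |

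**Would another clock explain it?** Time 1B from its first treatment, so that day 0 becomes treatment day 1, and add 1 to each 1B day:

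- PaO2/FiO2 becomes 1, 3, 5, which matches 1A.
- Ferritin becomes 3, 7, 10, 15 against 3, 6, 9, 14. The first matches and the other three are a day late.
- Banked blood on days 4 and 8 becomes 5 and 9 against 5 and 8. The first matches and the second does not.

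Timed from the first exchange, the pattern reverses: the later samples match and the early ones do not. No single clock fits all rows. The ferritin row splits within itself.

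**Exchanges completed at each affected follow-up sample**

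| Sample | 1A | 1B, drawn before that day's exchange | 1B, drawn after |
|---|---|---|---|
| Second PaO2/FiO2 (day 3 v 2) | 2 | 1 | 2 |
| Third PaO2/FiO2 (day 5 v 4) | 3 | 2 | 3 |
| First ferritin (day 3 v 2) | 2 | 1 | 2 |
| First banked sample (day 5 v 4) | 3 | 2 | 3 |

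So 1B has one exchange fewer (1/2 = 50% or 1/3 = 33% fewer) or none fewer. The documents do not say which, because draw timing on exchange days is not stated for these rows. Even with equal counts, a 1B sample would follow an exchange on the same day, while the 1A sample comes a day later. The first PaO2/FiO2 runs the other way: an exchange day in 1A (day 1), a non-exchange day in 1B (day 0).

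**Day 28.** Both tables mark physical examination and banked blood. 1B alone also marks eight rows: CBC, BMP, CRP, cytokine panel, GM-CSF, two respiratory rows and ruxolitinib dosing. That means day-28 laboratory tests for up to 10 patients in 1B and none in 1A.

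**Dosing marks.** Days 0 to 14 are 15 days, and day 28 makes 16 marks, against a stated total of 14 days.

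**Response window.** Through day 14 the cytokine draws are 1 + 14 + 5 = 20 in 1A (screening, daily, post-exchange repeats) and 1 + 15 + 5 = 21 in 1B. The one extra draw is day 0, which could enter the peak value.

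**The case against.** The strongest reply is that little hangs on this. The exchange clock is the same in both tables. The daily panels agree on all of days 1 to 14, which covers the response window. PaO2/FiO2 is not a named endpoint, and daily SpO2 and FiO2 remain available for ventilated patients. The cohorts are sequential, with 10 patients each, for hypothesis generation, and the only comparison between groups that the plan spells out is for safety. The day-28 marks may be a fill-through or extraction error, since they include drug dosing. All of this stands, and it limits the point.

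A reader might go further and infer that the two cohorts run on different clocks, that ferritin and banked blood cannot be compared at all, or that the offset would pass for a ruxolitinib effect. The documents support none of these. The exchange rows agree. Ferritin matches on days 6, 9 and 14, and banked blood on days 8 and 28. No direction of bias can be shown: if a measure improves over time, earlier 1B values would look worse and could hide a benefit. Nor can late cytokines be said to exist only in 1B, since banked blood is marked on day 28 in both cohorts.

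What the reply does not answer is that no clock makes the 1B rows consistent, and that the text sends staff to these tables.

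**Conclusion.** The 1B table is wrong as written in specific rows. Day-matched comparison is lost for all three PaO2/FiO2 values (ventilated patients only), for the first on-study ferritin and for the first on-study banked sample. It is kept for the later ferritin and banked samples and for the daily cytokine panels through day 14. The fibrinogen mark on day 10 contradicts the text. The day-28 laboratory marks differ between cohorts and sit badly with a possibly virtual visit, as does the day-28 banked sample in both cohorts. The ruxolitinib dosing marks conflict with the stated total; the passages must be reconciled, and this review does not say which is right.

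The size and direction of any bias cannot be given. The difference in completed exchanges is zero or one, depending on draw timing. The pattern looks like marks left in place when day 0 was inserted, but that cause is an inference. The reading rests on tables extracted from PDF. The 17-cell rows and the agreement of the TPE rows with the text support it, but the 1B day-28 column needs checking against the source page.

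**What to change.** Check the 1B day-28 column against the source page first. Then amend Appendix B:

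1. Put PaO2/FiO2, the first ferritin and the first on-study banked sample on the same days relative to the first exchange in both tables. If 1A has already been sampled, moving the 1B marks keeps its data usable.
2. State whether these samples are drawn before or after the exchange when they fall on an exchange day.
3. Remove the day-10 fibrinogen mark in 1B, or reconcile it with the text.
4. Make the day-28 laboratory marks the same in both cohorts and consistent with a possibly virtual visit. Say what happens to the banked sample, marked in both, when the visit is remote.
5. Reconcile the ruxolitinib dosing marks with the Treatment Plan.

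The cost is a table amendment, ideally before cohort 1B opens. The number of samples is unchanged or falls, unless day-28 laboratory tests are added to 1A; that would mean up to 10 further patients tested in person.
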